4. PROTECTION OF HUMAN SUBJECTS

Ethical considerations

The study will be conducted according to ethical principles stated in the Declaration of Helsinki (2013). IRB approval will be obtained before initiating the study. Assent and permission forms will take into consideration the well-being, free-will and respect of the participants, including respect of privacy.

Sources of Information.

RCT measures will be collected at baseline, intervention end, and 3-months post-intervention end in online surveys. All participants, regardless of study condition, will provide data at each time point. FG and CAT data will be collected online.

4.a. Potential Risks

The largest risk posed by participation in the study is inadvertent loss of confidentiality of one's bullying behavior or experiences. Confidentiality also may be lost if someone sees the participant's computer screen or intercepts his/her cell phone and reads the text messages. It is possible that survey questions or intervention topics may cause discomfort for some youth. It also is possible that conversations between Text Buddies will be harmful (e.g., bullying) in the RCT. Finally, it is possible that participants in the focus groups might be in the same online focus group as their bully.

4.b. Adequacy of Protection against Risks

The researchers take these potential risks very seriously. The PI will be responsible for all aspects of the project with respect to intervention design, data collection, and use of data. All aspects of the study will be approved by Pearl IRB, the Center for Innovative Public Health Research (CiPHR)'s OHRP-approved IRB of record prior to commencing data collection.

Informed Youth Assent and Caregiver Permission.

Youth assent and parental permission forms will receive final approval from the IRB before going into field. The assent information will be discussed with the participant by study staff either online, or at school or BCGA Clubs if youth are back in person. who are trained in Human Subjects Protections. Participants will be given the opportunity to ask any questions. They will be told that they can choose not to participate without any consequence. Given that children are a

vulnerable population, we also will be collecting active parental permission.

Because the study is low-risk, we will be sending the forms home for the parent and child to complete. To ensure that youth with language difficulties are able to understand the information they are being provided, the assent form will be written below the 6th grade level.

To further facilitate the ease of recording one's choice, we may offer the option to indicate one's acceptance or declination of youth assent and parent permission via an online form (i.e., that a clicked "yes" will be sufficient). Accordingly, we are requesting a waiver of documentation of youth assent and parent permission for those who complete an online form because the study involves minimal risk.

We will assent youth the same way that we are obtaining parental permission unless it is explicitly stated and documented otherwise.

Phone numbers for Drs. [name] and [name], and Pearl IRB will be listed in the assent and permission forms in case a participant or a parent has a question or would like to discuss the study or any concerns.

We may employ a passive parental permission protocol for youth recruited from the Boys and Girls Clubs, and also are requesting a waiver of parental permission for those recruited via social media. We are requesting this because:

1. The research involves no more than minimal risk to the subjects.
2. The waiver or alteration will not adversely affect the rights and welfare of the research participants.
3. It would not be possible to do this research with active signed parent/guardian permission. In the case of the Boys and Girls Clubs, only 50% of active permission forms given to eligible youth were returned. In the case of social media, obtaining parental permission would be logistically impracticable.
4. Due to the longitudinal nature of the research, identifiable private information is required to follow youth over time.
5. Whenever appropriate, the subjects or legally authorized representatives will be provided with additional pertinent information after participation
6. For the Boys and Girls Club youth, participant selection is based on club membership and not exclusionary.

Youth who are recruited online will provide verbal assent during the enrollment call and again provide assent at the beginning of the baseline survey. Youth recruited via Boys and Girls Clubs who are enrolled using a passive parental permission protocol will have the opportunity to ask questions when the study activity is initially introduced to them. Because the forms will be handed directly to parents, they will have the opportunity to ask questions about the study at that time. If either caregivers or youth have questions subsequently, they can utilize the contact information provided on the form to reach Drs. [name] and [name].

Protection against Risk.

Reports will only use aggregated data. No report of individual data will be provided. The core research team will have monthly meetings, and more frequently when in field; and will utilize real-time Internet technology to monitor the progress of the study.

Research staff will help the participants set their phones to be password protected to limit access by others if they would like. We also will provide instruction on how to change their phone settings so that text messages do not scroll across the screen as an alert. Youth will be encouraged to only read messages when they are in a private space where they feel like they can engage with the content safely. We also will encourage youth to delete any messages that they do not want others to read.

Youth will be encouraged to complete the online surveys in a private space where no one can see their screen. They will be able to pause and come back to the survey later if they are not in a safe place.

Participants will be told in the enrollment meetings and in the assent form that some survey questions and program messages may make them feel uncomfortable. They will be encouraged to skip such questions or messages. They will also be told that they may withdraw from the program if they choose.

Because we are recruiting only about 7 youth per school into the male and female focus groups, respectively, we think it is very unlikely that a bully victim's buddy will be in the same focus group. Nonetheless, we will make it clear that participants can reach out to us at any time and stop their participation, including if they are uncomfortable with the other people who are taking part in the focus group.

Monitoring of Text Buddy Communication. Text Buddies are paired intervention participants who will be encouraged to text message each other about to discuss program content throughout the intervention. For example: “Talking about your bullying experiences with friends can be hard. Now that you’re equipped with mad communication skills, try talking with your Buddy about the most recent time you saw someone bullied. What did you do? How did you feel? Text your Buddy and share.”

Buddies will be paired based on sex and school / setting so that they will be at different schools / settings based upon findings from the earlier beta test. The software program will identify youth who match on these criteria and automatically pair them. Those who are not automatically paired will be flagged so that the research team can manually pair youth.

We posit that social support from a Text Buddy will positively influence youth over time. However, balancing this with the privacy needs of our participants, who likely do not want to exchange contact information with a stranger, is important. As such, all Text Buddy messages are routed through the study server, replacing the need for this exchange. Participant cell phone numbers will never be distributed to other participants. To send a message, participants will simply text the dedicated BuddyLine, the program phone number that participants will use to communicate with their Buddy. This message is sent directly to the program server, which identifies the intended recipient, and routes the message to the assigned Text Buddy. This methodology will also allow us to measure the amount of interaction between Buddies accurately; if participants texted each other directly, we would have to rely on self-report to measure frequency of contact. For analysis, we will keep a count record to reflect the number of messages sent by each participant.

Prior to the program start, we ask intervention participants to agree to a Text Buddy Code of Conduct that sets clear expectations for healthy interaction and support. We have closely monitored the interactions between Buddies during the beta test and did not see any inappropriate interactions. We also will block messages that contain specific key words (e.g., racial epithets, drug names, participant contact information such as social networking profile names) for review before they are sent through to the Buddy. Study staff **closely monitor** the Buddy interactions (16 hours/day) while in field.

Concerning message content is elevated to the PI within 24 hours. Study staff are assigned to monitor the messages in real time from 8am – 10pm pacific standard time. Staff are able to receive text message alerts on their phone when a Buddy message is detected should they be away from their computer during their monitoring session. We note that across three projects that [name]’s team has implemented this feature, never has there been a case of on buddy bullying another.

Providing resources and referrals. This is not a mental health intervention. Nonetheless, we will provide resources and referrals for youth. For example, we will have a resource page on the intervention website for youth who are upset or need help. The 24-hour crisis hotline, [name], will be listed in case youth require immediate intervention. Those who are experiencing thoughts or feelings that are upsetting will be referred to the National Information Mental Information Center for assistance identifying a treatment provider. The National Mental Health Information Center is funded by the Center for Mental Health Services within the Substance Abuse and Mental Health Services Administration (SAMHSA). As one of SAMHSA’s clearinghouses, the Center provides mental health information and treatment referrals to a varied audience throughout the United States and its territories, via the toll-free number [contact]) and website (www.mentalhealth.samhsa.gov) that offers a service locator for finding local resources.

If someone articulates a plan to hurt themselves or others when monitoring Text Buddy messages or other participant program interactions, we will advise them to call 911 or go to their nearest emergency room. We also will provide the suicide crisis hotline. If crisis language is observed during monitoring, youth will be referred to [name], LICSW, for assessment and referral. [name] has extensive experience implementing this type of crisis contact for youth taking part in research studies. She is the clinician on call for [name] and Growing up with Media studies. She has also served as consultant for studies measuring child sexual and physical abuse.

Protecting privacy. [name] team has conducted several online national surveys with very sensitive questions. There are many benefits to this methodology, including increased self-disclosure compared to interviewer-based data collection, and convenience and increased safety for the participant as s/he can decide when and where to best answer the survey. Participants will be given the option to complete the survey on their own, or at school or the Club if they are back in brick and mortar settings. Participants will receive a personalized link which they can click on to take them directly into the survey. To further ensure privacy, we also ask participants to complete the survey in a private place – and then ask again at the beginning of the survey to see if they are. If they indicate they are not, they are encouraged to pause the survey and come back to it later.

No names will be collected except on youth assent and parent permission forms. Study materials will be safeguarded as follows: informed parent permission and youth assent forms will be kept under double lock in filing

cabinets in separate physical locations. Secure UNC SOE server if not physically collected.

Secure electronic transmissions and storage of data. All data are password protected with strong encrypted passwords and is transmitted securely using SSL (TLS) 128-bit encryption across the Internet (HTTP). SSL provides front-end users with the assurance of access to a valid, “non-spoofed” site and prevents data interception or tampering with sensitive information. The 128-bit encryption is the preferred security level of government and financial institutions. To ensure against the remote possibility that an intruder gains access to stored data, all data stored are protected with strong passwords that are also encrypted, making use of any acquired data nearly impossible. Any Personally Identifiable Information (PII) is securely encrypted and stored separately from study data. All access to participant data is limited to access via a secure VPN network, making it impossible to access otherwise.

Data are located on our dedicated server in Liquid Web's secure SSAE-16 Compliant datacenter in Lansing, Michigan. Dedicated servers eliminate security issues involved with shared hosting environments where hundreds of websites and users reside on one shared web server, as well as ensuring both physical and network security.

Dedicated server facility security includes:

- 24/7/365 Manned Facilities
- CCTV Security Cameras Covering Inside, Outside and All Entrances of Data Centers
- Site Entrances Controlled By Electronic Perimeter Access Card System
- Sites Remotely Monitored By 3rd Party Security Company
- Entrances Secured by Mantraps with Interlocking Doors
- SSAE-16 & HIPAA Compliant, Safe Harbor Certified

Having a backup copy offsite is critical for protecting against data loss due to a catastrophic event (e.g., an earthquake). The datacenter is equipped with redundant tier 1 bandwidth, ensuring minimal latency and fast connections to all points of the global Internet. Datacenter access is strictly limited to technical staff. Electronic security systems control datacenter access and are accompanied by a full complement of motion-detecting security cameras that monitor the entire facility.

Our servers are equipped with daily backups to an external hard drive, as well as extensive server-hardening, firewall protection, brute force detection and evasion, Apache denial-of-service attack prevention/protection, and email virus filtering. In addition, the server is monitored by Liquid Web 24/7 to ensure 100% uptime and receives daily security audits and monthly vulnerability scans.

A description of the text messaging platform. To further promote data security, the BullyDown program is delivered through CiPHR's proprietary platform that has been developed and improved upon over several research projects (e.g., R01 TW007918, R21 CA135669, R01MH096660 R34MH109296, R34MH108781, R01 HD095648). The system was developed using PHP, Javascript and Jquery programming languages and utilizes MySQL Databases running on a Linux (LAMP) based server. The system makes use of the Twilio gateway service's API to both send and receive text messages.

4.c. Potential Benefits of the Proposed Research to the Participants and Others

Extant research has demonstrated the link between incidence of school bullying and resulting adverse outcomes such as depression, anxiety, physical illness, school dropout, and suicide. Research also has identified a link between school bullying behaviors and high-intensity violence in schools (e.g., school shootings). To the extent that the BullyDown text messaging program is effective in reducing bullying in schools, we anticipate positive long-term societal effects for youth, including decreased need for delinquency and mental health services, enhanced positive youth development, improved academic achievement, and societal cost savings associated with these outcomes.

4.d. Importance of the Knowledge to be Gained

BullyDown will contribute to scientific knowledge in several important ways: 1) BullyDown will be delivered outside of school. By engaging with the content in a non-academic setting, youth may be more likely to apply their new behaviors across contexts, including bullying scenarios that take place online and other places where youth congregate. This also has the advantage of giving youth the opportunity to learn SEL components and interact with someone else in the program (i.e., a Text Buddy) without a potential perpetrator sitting in a desk nearby. It also bypasses situations when school-based programming is not viewed as "cool" by some students, resulting in their under-engagement in program activities, which

can implicitly reinforce negative social norms. 2) In school-based intervention programs, school personnel are often called upon to implement the content. To do so, they need to be extensively trained to maximize efficacy. Increasingly, financial resources for training are simply not available in US public schools. BullyDown is administered through text messaging, bypassing training and competition with professional development time. 3) Compared to in-person interventions which may be vulnerable to variable implementation fidelity, all youth in the program receive the same content in the same order, thereby ensuring fidelity. Also compared to “apps” that require a smart phone and data, all cell phones are text messaging-capable. 4) The meta-analytic results described above reflect the best-case scenario. Although all states require schools to implement bullying prevention programming, there is significant variation in what is mandated, resulting in a wide spectrum of programming offered in schools across the US. In the FGs we conducted in the BullyDown development process, very few youth talked about a comprehensive bullying prevention curriculum in their school. BullyDown can be delivered as a “booster” outside of school time that enhances whatever programming is being offered by schools. In doing so, one of the benefits of BullyDown is that it helps to ensure all youth are exposed to the basic tenets of a bullying prevention curriculum. 5) Given the focus on victimization that most of the current prevention programs have, our focus on perpetration is innovative.

4.e. Data and Safety Monitoring Plan

The PI will be responsible for all aspects of the project with respect to intervention design, data collection, and use of data. Pearl IRB will approve all aspects of the study prior to commencing data collection. Informed youth assent and parental permission will be obtained from all participants. Participants will have access to 24-hour referral information as well as phone numbers for the study administrators (i.e., PI and IRB).

Data Monitoring

The PI will be responsible for monitoring data to ensure the safety of participants. Additionally, the IRBs will be responsible for data and safety monitoring.

In order to ensure privacy for participants and to minimize risk, we will be using computer- and text messaging-based data collection procedures. This reduces the number of people who view the data and increases self-disclosure on sensitive topics. Access to the data will be password protected.

Each participant will be given a random unique identifier in the data set which will be stripped of all personal information to protect confidentiality. Datasets used for analysis will contain project identification numbers but neither names nor other identifying information such as email addresses. Identification information will be retained by CiPHR for the duration of the study and stored separately from the responses provided by subjects.

Collaborators will receive data stripped of personal identifiers. To ensure complete confidentiality, access to the key linking personal identifiers to usernames and passwords will be restricted to key personnel. Reports will not identify individual adolescents. [name] will oversee the data storage and reporting procedures. Upon completion of the analysis of the data collected in this study, records will be destroyed. Reports will only use aggregated data. The core research team will have weekly meetings utilizing real-time Internet technology to monitor the progress of the study.

Adverse Events

[name] will review the progress of the project and data being collected to ensure that potential adverse effects are identified, if they occur, and reported to both IRBs. This includes unanticipated problems involving risks to subjects or others. Any action recommended by the IRBs to the PI will be implemented immediately in order to minimize further risk. The adverse event report will further be communicated to other entities (e.g., NIH) in a timely manner as appropriate based on their policies. [name] will also be responsible for reporting to the project officer if the IRBs or any other entity temporarily or permanently suspends an NIH-funded trial. All notifications will be done via email immediately followed with a certified letter.

References

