Beta test: Based upon the enrollment experience and our plan to ensure text buddies in the intervention arm are paired with people at different schools/settings, it may be difficult to fully randomize all new beta test participants. In this case, we may randomize some youth to the intervention or control group, and then purposefully assign other youth to the intervention.

Retention strategies.

In her 36-school longitudinal study, [name] had a retention rate of 88% at 12 months.⁹⁸ Our BullyDown beta test

had a 100% retention rate at one-month post-intervention follow-up. We anticipate a similarly strong retention rate at 3 months post-intervention end in the current study. To achieve this, we propose:

Incentives. All youth recruited via schools or Boys and Girls Club via active parental permission will receive \$5 for returned parental permission and youth assent forms irrespective of whether permission was granted.

Research participants in the FGs and CATs will each receive \$30 for their participation. The FG participants will receive \$15 for each day they participate. CAT participants will receive \$15 for returning their feedback on the text messages and \$15 for taking part in the online discussion. Youth in the beta test will receive \$25 after they complete the Intervention end survey. Those in the RCT will receive \$15 for each survey they complete for a total of up to \$45. Incentives will be fulfilled with Amazon gift cards because they can be distributed online, monitored to ensure that they have been used, and reissued if necessary. These incentives are separate from the incentive provided for the returned parental permission form.

Each school and Club may be given a \$500 stipend for their participation each year; all organizations taking part in the RCT will be given the stipend. Teachers will not receive any compensation or incentive directly.

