Integrating lessons learned into the content. Several participants in the beta test expressed confusion regarding the interactive Text Buddy feature. Further probing revealed that some of this was related to feelings of discomfort about discussing bullying with students they went to school with. Nonetheless, beta test participants sent between 0-52 messages to their Text Buddy, suggesting its acceptability potential. To improve the experience, we will expand the instructions for the Text Buddy feature and include more concrete prompts about what Buddies can talk about with each other (e.g., Maybe text your buddy and talk about what you think it would be like if you stood up for a friend being bullied at school tomorrow). We also will match youth with someone at a different school/setting and make sure that they are aware of this so they do not worry they are talking with a classmate they may know.

Drafting attention matched control content. In the beta test, the control group received two messages a week focused on thanking them for being in the study. As has been done in [name] other interventions (e.g., R21 CA135669; R34MH109296), we will draft attention-matched content to well position this R21 for a competitive R01 submission. To ensure that youth in both arms receive the same 'attention,' content will address healthy lifestyle topics unrelated to bullying (e.g., fitness, nutrition).

Confirming adapted content for acceptability in Content Advisory Teams (CAT; n=70). The content will next be reviewed by a CAT comprised of ~24 students. Each CAT member will have one week to review the messages and provide feedback through an online platform. Next, an online group discussion will elicit reactions to the messages and program design. Possible questions include: How well do these messages speak to the experiences you and your friends have around bullying? How clear do you find the messages? How could we say things differently to make the messages more understandable? Once feedback from the CAT has been integrated, a second 24-member CAT of different students will confirm that the content has been improved. For instance, in a previous intervention development [name]'s team led, the second CAT noted that we included too many emojis, which we had added based upon feedback from the first CAT. Having two different groups review the content also ensures a wider range of opinions and feedback. The control content will be reviewed by a ~24-member CAT.

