Conducting a beta test to confirm the protocol, including the software functionality and surveys. Before rolling out the RCT, we may conduct a beta test to pilot the recruitment, enrollment, data collection, and randomization procedures, as well as to identify final opportunities to improve the content. In most cases, five is a sufficient number of testers to identify any issues. Here, we propose 15-20 youth so that ~10 youth will test the functionality of the intervention program and ~5 the functionality of the control program. Usability data will be collected weekly via text messaging from participants. We may send questions weekly via text messaging, or by phone for non-responders, about the program experience. At the end of the beta test, we may conduct one-on-one interviews to identify any additional experiential issues that need to be addressed before the RCT is launched.

Pilot RCT of BullyDown (n = 150)

Randomization and group assignment. Once youth complete the baseline survey, they will be randomly assigned to either the intervention (n = 76) or the control (n = 74) group. We will use a computerized minimization technique, as originally described by Taves⁵⁹ and more recently reviewed by others,⁶⁰⁻⁶² to balance the sample on youth key indicators. These may include sex, school or Club, and bullying perpetration history. Treatment assignment will be generated and maintained at a password-protected Internet website monitored by [name].

Contamination. Studies across participant populations and behavioral targets report that contamination is uncommon and does not affect study outcomes.^{63,64,65,66} Give this, and to be efficient with R21 resources, students will be randomized at the individual rather than school or Club level. As we have done previously,^{63,64} we will ask questions at intervention end that are specific to the BullyDown content. If indicated, we will include the number of correct exposure

questions as a proxy for contamination in multivariate models.

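### The behavioural arm comparisons would normally omit the minimization factors and ignore the intervention-only Text Buddy pairs, so their standard errors are slightly off in a direction the documents do not settle

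*Combined protocol and SAP*

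**What the plan says.** **Allocation.** Section 3C (Randomization and group assignment) has youth "randomly assigned to either the intervention (n = 76) or the control (n = 74) group" by computerized minimization. The candidate balancing factors are sex, school or Club, and history of bullying perpetration. They are named provisionally.

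**Covariates.** Section 3E tests baseline covariates for imbalance and carries the significantly imbalanced ones into the multivariate models. Otherwise covariates enter after the gross estimate, to examine mediation, and sex enters through a group-by-sex interaction. Nothing requires the minimization factors in the arm comparison.

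**Models.** Section 3E names logistic regression for the behavioural outcomes, and a GEE with exchangeable correlation across the follow-up periods. The GEE handles repeated measures on one youth. Neither model names the Buddy pair.

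**Pairing.** Section 4.b (Monitoring of Text Buddy Communication) says "Text Buddies are paired intervention participants who will be encouraged to text message each other". It also says "Buddies will be paired based on sex and school / setting so that they will be at different schools / settings". Section 3C, on the beta test, likewise refers to "our plan to ensure text buddies in the intervention arm are paired with people at different schools/settings", and 4.b says "we ask intervention participants to agree to a Text Buddy Code of Conduct". No Buddy is described for controls. The Buddy variable named for analysis is a message count: "For analysis, we will keep a count record to reflect the number of messages sent by each participant".

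**The concern.** Two features of the design are missing from the behavioural models, and they push the standard error in opposite directions.

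First, minimization makes the arms more alike on prognostic factors than simple randomization would. A model that omits those factors estimates its variance as if that balance had not been forced. The standard error is then too large and the test conservative. A rule that admits only significantly imbalanced covariates will almost never admit a factor that was minimized.

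Second, Buddies are encouraged to talk to each other about bullying, and 4.b expects a Buddy's support to influence youth over time. If that makes outcomes within a pair alike, the intervention arm carries less information than 76 independent youth, while the control arm is unaffected. A model that treats all youth as independent then gives a standard error that is too small.

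At stake is the precision attached to preliminary behavioural estimates that section 3E intends mainly for planning the later R01. That trial would also need to know the pair correlation if it keeps the Buddy feature, and the plan names no pair variable for analysis.

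**Working it through.** The plan states no alpha, power or pair correlation, so there is no figure of its own to reproduce. A two-sided 5% test is assumed.

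**Inputs from the documents.** Arms of 76 and 74, so at most 76/2 = 38 pairs. Bullying prevalence of 20-24% (section 1), taken as 22% for both baseline and outcome. An 80% retention threshold (section 3E).

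**Assumed inputs.** Pair ICC of 0 to 0.3. Outcome rates in baseline bullies versus others that are equal (not prognostic), 45% vs 15.5% (moderate), or 60% vs 11.3% (strong). The last two keep the overall rate at 22%: 0.22 × 0.45 + 0.78 × 0.155 = 0.220, and 0.22 × 0.60 + 0.78 × 0.113 = 0.220.

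**Step 1: pairing alone.** Pairs of size two multiply the intervention-arm variance by 1 + ICC. So

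true / model variance = [(1 + ICC)/76 + 1/74] / [1/76 + 1/74] = 1 + (74/150) × ICC = 1 + 0.493 × ICC,

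and actual size = 2 × [1 − Φ(1.96 / √ratio)]. With 80% retention and independent dropout, a retained youth's Buddy is also retained with probability 0.8, so the ratio becomes 1 + 0.8 × 0.493 × ICC.

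| ICC | SE ratio, full retention | Size | SE ratio, 80% retention | Size |
|---|---|---|---|---|
| 0 | 1.000 | 5.0% | 1.000 | 5.0% |
| 0.05 | 1.012 | 5.3% | 1.010 | 5.2% |
| 0.1 | 1.024 | 5.6% | 1.020 | 5.5% |
| 0.2 | 1.048 | 6.2% | 1.039 | 5.9% |
| 0.3 | 1.071 | 6.7% | 1.058 | 6.4% |

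**Step 2: omitted minimization factors alone.** If balanced factors explain a share R² of outcome variance, the ratio is about 1 − R². With baseline and outcome prevalence both 22%, R² is the squared difference in rates: (0.45 − 0.155)² = 0.087 and (0.60 − 0.113)² = 0.237. The formula then gives sizes of 4.0% and 2.5%. A weak factor (R² = 0.05) gives 4.4%.

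**Step 3: both together.** The ratio is about (1 − R²) + 0.493 × ICC. The two errors cancel at ICC = R²/0.493, which is 0.18 for the moderate factor and 0.48 for the strong one.

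**Step 4: simulation at full retention.** Setup: 150 youth, minimization on sex, three schools and baseline bullying, same-sex different-school pairs, no arm effect, 20,000 trials per setting (Monte Carlo SE about 0.15 points). Size of the planned unadjusted test:

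| Baseline bullying | ICC 0 | 0.05 | 0.1 | 0.2 | 0.3 |
|---|---|---|---|---|---|
| Not prognostic | 4.8% | 5.0% | 5.8% | 6.2% | 6.6% |
| Moderate | 3.8% | 4.2% | 4.0% | 4.5% | 5.0% |
| Strong | 2.4% | 2.6% | 2.8% | 3.0% | 3.2% |

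In 10,000 minimized trials no minimization factor was ever imbalanced at p < 0.05, so the imbalance rule would not have brought one in.

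**Step 5: candidate remedies, full retention.**

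- Pair clustering without adjustment: 4.4-4.8% (not prognostic), 3.4-3.6% (moderate), 2.2-2.5% (strong).
- Adjustment ignoring the pairs, at ICC 0.3: 6.8%, 6.6% and 6.0% respectively.
- Both: 4.4-4.8%, 4.3-4.6% and 4.2-4.7%.

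At 80% retention, doing both gives about 3-5% (3.2-4.6% in one run), so it is mildly conservative.

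**The case against.** **The strongest case against acting** is that the planned test is mostly at or below its nominal level. In the simulation table 12 of 15 settings are at or below 5.0%. The three above it need both an ICC of at least 0.1 and a baseline bullying history that does not predict later bullying, although the plan itself lists that history as a candidate balancing factor. Complete-case analysis with dropout breaks pairs and shrinks the effect further. No alpha or power is claimed for the behavioural outcomes. All of this stands and is why the point is of low severity.

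**A reader might infer that pairing in one arm inflates the false-positive rate.** The documents do not support that. They give no pair ICC, and it may be near zero: Buddies attend different schools or settings, and "beta test participants sent between 0-52 messages to their Text Buddy", so some sent none. An equal benefit to every paired youth creates no within-pair correlation. Inflation under the null also needs Buddies to shift each other's outcomes while the programme has no net effect. If the programme does nothing at all, pairing leaves the test at or below nominal. Interval width is the more relevant consequence.

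**A reader might also say the plan adjusts for nothing but imbalanced covariates.** That is too strong: covariates also enter for mediation, and sex enters through the interaction. Neither is a prespecified adjustment of the arm comparison for the minimization factors.

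**The remedy has limits.** Section 3B anticipates about seven schools and two Clubs across activities. With nine sites entered separately at 80% retention, the logistic fit failed in about 38% of simulated trials, so sparse sites must be collapsed. Collapsing was not itself simulated with a prognostic site.

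**Conclusion.** The point holds as a modest one. The better supported half is the covariate rule: it would leave out the minimization factors and make the unadjusted test conservative if baseline bullying is prognostic, at about 2.4-4.4% actual size with no pair correlation. The other half is conditional: with an assumed positive ICC of 0.05-0.3, ignoring the pairs makes standard errors about 1-7% too small at full retention and about 1-6% at 80% retention.

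The net direction depends on the ICC, the prognostic strength and the factors finally used, none of which the documents fix. A reader might take this as bias in the intervention effect or as a threat to the trial's main conclusions. It is neither: pairing does not bias the arm estimate, and feasibility and acceptability are judged against thresholds that these models do not touch. The size figures rest on the assumed 22% prevalence, three schools and prognostic strengths.

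**What to change.** 1. Replace the significance-based covariate rule with prespecified adjustment of the behavioural models for the minimization factors actually used, including baseline bullying and sex. Collapse sparse sites, for example to school, Club and social media. Report the gross estimate alongside.
2. Keep the Buddy pair ID, including manually made pairs, in the analysis file. The server already holds this link, since it is the server "which identifies the intended recipient, and routes the message to the assigned Text Buddy".
3. Report small-sample-corrected standard errors clustered on the pair, with each control and each unpaired youth as a cluster of one. Cluster the longitudinal GEE on the pair too.
4. Do not cluster on the pair without the adjustment in item 1, because that alone makes a conservative test more so.
5. Report the pair ICC descriptively with its interval. For R01 planning use an assumed range (for example 0 to 0.3), not the imprecise pilot value alone.

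**Cost.** Some wording in section 3E and one exported variable. Intervals widen slightly, the adjusted odds ratio is conditional, and the test is mildly conservative. Simulated power at ICC 0.1 and an assumed conditional log odds ratio of −1, planned test versus adjusted and pair-clustered, is 55.5% vs 51.6% if baseline bullying is not prognostic, 50.2% vs 50.2% if moderately so, and 40.0% vs 46.5% if strongly so. The first comparison is not at equal size: the planned test there runs at 5.8%.
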